12.4.1 Analysis Population

A total of 9 patients will be treated in the Phase I component with the first at the starting dose of 200 $\mu g/kg/d \times 4$ wks. If the regimen proves too toxic or if none of the dose levels appears to reach 30% DLT, fewer patients may be treated.

Table 12.1

		Cumulative Number of Patients Treated at This Dose								
		1	2	3	4	5	6	7	8	9
	0	E	E	Е	Е	Е	Е	E	Е	Ε
_	1	D	S	S	S	S	Е	E	Е	Е
.	2		U	D	S	S	S	S	S	S
umber Dose	3			U	U	D	S	S	S	S
E O	4				U	U	U	D	D	S
z "	5					U	U	U	U	U
를 Œ	6						U	U	U	U
mulat Ts at	7							U	U	U
Ē º	8								U	U
ರ ದ	9									U

12.4.2. Analysis Plan

Since our primary objective in the Phase I component is to ascertain whether the highest dose is tolerated with acceptable side effects, this will be completed using the schema described in Table 12.1.

12.4.3.

Patients will be followed clinically, by ECG, and laboratory measures to ensure that no serious adverse effects occur and that safety is established at the proposed treatment doses.

12.5 Secondary Analysis

Our Primary objective in the Phase II component is to assess progression free survival at 6 months.

12.5.1 Analysis Population

20 additional patients will be enrolled in the Phase II component of this study for determination of efficacy.

12.5.2 Analysis Plan

For the Phase II component, it is expected that no more than 50% of patients will have stable disease at 6 months (defined as stable MRI and clinical status, including being on a stable dose of steroids and not on bevacizumab). We will therefore consider this regimen of interest if significantly more than 50% of patients achieve this benchmark.

12.6 Sample Size

12.6.1 Accrual estimates

We expect to accrue the total number of 29 patients within the 36 month timeline proposed.

12.6.2 Sample size justification

In collaboration with our statistician, it was determined that our sample size of 29 total patients would substantiate enough power to reach our points of analyses.

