	for newly diagnosed glioblastoma GBM.
STUDY PHASE	I/II
INDICATION	Newly diagnosed glioblastoma
INVESTIGATIONAL PRODUCT OR PROCEDURE	Continuous infusion of Plerixafor
PRIMARY OBJECTIVE(S)	Efficacy as measured by progression free survival at 6 months
SECONDARY OBJECTIVE(S)	Safety of the continuous infusion of Plerixafor subsequent to irradiation
TREATMENT SUMMARY	200 micrograms per kilogram per day for four weeks, in second patient will increase to target dose of 400 micrograms per kilogram per day for four weeks, and continue treatment of subsequent patients at the target dose if tolerated.
SAMPLE SIZE	29 patients
STATISTICAL CONSIDERATIONS	Dose-escalation study with planned dose levels using the modified toxicity probability interval (mTPI). For efficacy, a greater than 50% PFS at 6 mos. PFS will be considered a positive signal and warrant further study.

SCHEMA

*Infusion will last for either two or four weeks with Phase I dose determined per the adjustment rules described in section 12.1; Phase II dose and duration determined in the Phase I

LIST OF ABBREVIATIONS AND DEFINITION OF TERMS

ABW Actual Body Weight ADL Activities of daily living AE Adverse event CBC Complete blood count CMAX Maximum concentration of drug CNS Central nervous system CRF Case report/Record form CR Complete response CTCAE Common Terminology Criteria for Adverse Ever DLT Dose Limiting Toxicity DSMB Data Safety Monitoring Board ECG Electrocardiogram GBM Glioblastoma GI Gastrointestinal HIV Human Immunodeficiency Virus IBW Ideal Body Weight IRB Institutional Review Board IV Intravenous KPS Karnofsky Performance Score MTPI Modified Toxicity Probability Interval OS Overall survival PLT Platelet PD Progressive disease PFS Progression free survival	ts
AE Adverse event CBC Complete blood count CMAX Maximum concentration of drug CNS Central nervous system CRF Case report/Record form CR Complete response CTCAE Common Terminology Criteria for Adverse Ever DLT Dose Limiting Toxicity DSMB Data Safety Monitoring Board ECG Electrocardiogram GBM Glioblastoma GI Gastrointestinal HIV Human Immunodeficiency Virus IBW Ideal Body Weight IRB Institutional Review Board IV Intravenous KPS Karnofsky Performance Score MTPI Modified Toxicity Probability Interval OS Overall survival PLT Platelet PD Progressive disease PFS Progression free survival	ts

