12.6.3 Effect size justification

This is a single-arm (non-randomized) study, therefore the historical control rate has been used to

determine our effect size justification.

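### Section 12.6.2 claims enough power for 29 patients with no test, alpha or target rate; an exact 5% test against 50% in the 20 Phase II patients would usually miss true rates below about 72%, and the synopsis states a different rule

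*Combined protocol and SAP*

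**What the plan says.** Section 12.6.2 is the whole sample size justification. It says that, in collaboration with the statistician, "it was determined that our sample size of 29 total patients would substantiate enough power to reach our points of analyses". It gives no test, alpha, target rate or power figure. Section 12.6.3 adds that, because the study has a single arm, "the historical control rate has been used to" determine the effect size justification. That section prints no rate.

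The 29 patients have two parts. Section 12.4.1 says "A total of 9 patients will be treated in the Phase I component", and 12.5.1 says "20 additional patients will be enrolled in the Phase II component of this study for determination of efficacy".

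The efficacy criterion is in 12.5.2: "it is expected that no more than 50% of patients will have stable disease at 6 months", and "We will therefore consider this regimen of interest if significantly more than 50% of patients achieve this benchmark". Section 12.4 carries the same text, and 12.7 makes it the condition for moving to future studies. The statistical considerations row of the synopsis words it differently: "For efficacy, a greater than 50% PFS at 6 mos. PFS will be considered a positive signal and warrant further study". That wording has no significance condition.

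**The concern.** A claim of enough power means something only against a stated test, error rate and true rate worth detecting. None of these is given, so the claim cannot be reproduced. It is also attached to 29 patients, although the efficacy test is assigned to 20.

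The go/no-go decision rests on this test. If 20 patients can reliably detect only a very large gain over 50%, a moderate improvement will usually fail the criterion in 12.7. The section on sample size would meanwhile tell the reader that the trial was large enough to find it. The synopsis rule has the opposite weakness: it passes easily, including when the true rate is exactly 50%.

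**Working it through.** **Inputs from the plan.** Efficacy n = 20 (12.5.1). Phase I n = 9 (12.4.1). Total 9 + 20 = 29, which agrees with 12.6.2 and is the only figure there that can be checked. Null rate 50% (12.4, 12.5.2, 12.7).

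**Assumptions.** The plan asks only for significance. I take an exact binomial test at 5%, one- or two-sided, with all 20 patients evaluable, and then vary the test, alpha and n.

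**Cut-off.** Find the smallest r with P(X ≥ r | n = 20, p = 0.5) ≤ alpha.
- P(X ≥ 14) = 60,460 / 1,048,576 = 0.058, above 0.05.
- P(X ≥ 15) = 21,700 / 1,048,576 = 0.0207, below both 0.05 and 0.025.

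The bar is therefore 15 of 20 (75% observed) whether the 5% is one- or two-sided. The actual one-sided false-positive rate is 2.1%.

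**Power.** P(X ≥ 15 | n = 20, p):

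| True rate | Power |
|---|---|
| 60% | 12.6% |
| 65% | 24.5% |
| 70% | 41.6% |
| 75% | 61.7% |
| 80% | 80.4% |

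Solving for p, power is 50% at a true rate of 72.1% and 80% at 79.9%.

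**Other readings of the significance test.**

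| Reading | Cut-off | False-positive rate | Power at 70% | True rate for 80% power |
|---|---|---|---|---|
| n = 20, exact, one-sided 10% | 14/20 | 5.8% | 60.8% | 75.5% |
| n = 20, uncorrected z-test, one-sided 5% (14/20: z = 1.79, p = 0.037) | 14/20 | 5.8% | 60.8% | 75.5% |
| n = 29, exact, two-sided 5% | 21/29 | 1.2% | 47.9% | 77.1% |
| n = 29, exact, one-sided 5% | 20/29 | 3.1% | 63.6% | 74.0% |

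The 80% power point is therefore about 74-77% in these readings. It falls further, to 70.8%, only if two lenient choices are combined: all 29 patients pooled and a cut-off of 19/29 (exact one-sided 10%, or an uncorrected z-test at one-sided 5% with z = 4.5/2.693 = 1.67). The exact false-positive rate is then 6.8%.

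**Synopsis rule.** Above 50% of 20 means at least 11. P(X ≥ 11 | 20, p) is 41.2% at a true rate of 50%, 75.5% at 60%, 87.8% at 65% and 95.2% at 70%.

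**How often the two rules disagree.** They give opposite decisions at 11, 12, 13 or 14 successes. The probability of that range is the difference of the two tails:
- true rate 50%: 41.2 − 2.1 = 39.1%
- true rate 60%: 75.5 − 12.6 = 62.9%
- true rate 70%: 95.2 − 41.6 = 53.6%

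**The case against.** The figure of about 80% depends on a test and alpha that the plan does not state. With a 14/20 cut-off a true rate of 70% passes 61% of the time, and with 20/29 it passes 64% of the time. This stands. The results are conditional, and a flat statement that the trial reaches 80% power only at a true rate of 80% would go too far.

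A reader might infer that a useful regimen would usually be rejected. The documents do not support that wording, because they never say what gain is useful. At a true rate of 75% the regimen passes 62% of the time even under the 15/20 rule, and under the synopsis rule most true rates above 50% pass easily. What the figures support is narrower: under a 5% exact test on 20 patients, true rates below about 72% would usually be missed.

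A reader might also infer that 12.6.3 sets the effect size equal to the 50% null. It does not say so. It says the historical rate was used in arriving at the effect size, and it prints neither the rate nor the effect.

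It can also be said that 12.7 calls this a pilot study, and that 12.6.2 speaks of several analyses, including a Phase I part where power is not the question. A small pilot is acceptable. The fault is to claim enough power for it while using a significance test as the gate to further studies. The Phase I part does not supply power for that test.

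**Conclusion.** The point holds as a missing justification and an unreconciled decision rule. The plan prints no power figure, so none is contradicted.

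The claim in 12.6.2 is unsupported as written. Under an exact 5% test on the 20 Phase II patients, 80% power requires a true rate about 30 points above the null (79.9% against 50%). A 14/20 cut-off, or exact 5% testing of all 29 patients, lowers this to about 74-77%, still at least 24 points above the null. Pooling is also not the written plan, since 12.5.1 assigns efficacy to the 20 additional patients. Only the most lenient combination of pooling and cut-off brings it to about 71%.

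The synopsis rule has high power but a 41% false-positive rate, and it reverses the decision for 11 to 14 successes. These results assume a binary outcome known for every analysed patient. Missing outcomes counted as failures would lower all the pass rates.

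**What to change.** - **12.6.2 and 12.6.3:** delete the statement that 29 patients give enough power. State one decision rule with its test, alpha, cut-off and analysed set, and its power at named true rates. For example: at least 15 of 20 Phase II patients, exact binomial against 50%, false-positive rate 2.1%, power 42%, 62% and 80% at true rates of 70%, 75% and 80%. Say whether Phase I patients count.
- **Synopsis, 12.4, 12.5.2 and 12.7:** use that same rule everywhere, so that 11 to 14 successes has one meaning.
- **Reporting:** give the observed rate with its exact 95% confidence interval. It would be tempting to add to 12.7 that fewer than 15 successes leaves a true rate of 65-70% open. That should not be written, because it fails for low counts: the exact upper limit is 68.5% at 9/20, which excludes 70%, and 63.9% at 8/20, which excludes the whole range. The interval is enough.

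The cost is a change of wording and a less favourable stated power. No patients are added.

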12.6.3 Effect size justification

This is a single-arm (non-randomized) study, therefore the historical control rate has been used to

determine our effect size justification.

12.7 Criteria for future studies

This is a pilot study with the expectation that no more than 50% of patients will have stable disease at 6 months (defined as stable MRI and clinical status, including being on a stable dose of steroids and not on bevacizumab). We will therefore consider this regimen of interest if significantly more than 50% of patients achieve this benchmark and would move further to future studies should this benchmark be reached.

APPENDIX A: Participant Eligibility Checklist

Protocol Title:	A Phase I/II study of local field irradiation and temozolomide
	followed by continuous infusion Plerixafor as an upfront
	therapy for newly diagnosed glioblastoma GBM.
Protocol Number:	
Principal Investigator:	[name]
ject Information:	

II. Sub

Subject Name/ID:	
Gender: Male	Female

III. Inclusion/Exclusion Criteria

	Inclusion Criteria (From IRB approved protocol)	Yes	No	Supporting Documentation*
1.	Patients must have tissue confirmation of high grade (WHO Grade IV) glioma including but not limited to glioblastoma, gliosarcoma, glioblastoma with oligodendroglial features, glioblastoma with PNET features.			
2.	The patient must have post-operative contrast enhanced imaging (CT or MRI) unless only biopsy performed (in which case post-operative imaging is not routinely obtained. In these patients, the preoperative study will serve as baseline).			
3.	Patient should have surgery (biopsy, partial resection or gross total resection) and no additional anticancer therapy except the chemoradiation as specified in the protocol.			
4.	For those patients in which steroids are clinically indicated, there must be a stable or decreasing dose of			

	steroid medication for \geq one week prior to the start of infusion.		
5.	Patients must be between the ages of 18 and 75 years old		
6.	Patients must have Karnofsky Performance score ≥ 60.		
7.	Adequate organ function is needed at time of screening visit including: 1. ANC ≥ 1500 2. Platelets ≥ 100,000 ml 3. Creatinine ≤ 1.5mg/dl; Cr clearance should be > 50 mL/min 4. AST and ALT ≤ 3 times the upper limit of normal 5. Serum potassium, magnesium and calcium within normal limits (supplementation to maintain normal electrolyte levels is acceptable) 6. If female of childbearing potential, negative pregnancy test		
8.	The patient or his/her legal representative must have the ability to understand and willingness to sign a written informed consent document.		
9.	Patient agrees to use an effective method of contraception (hormonal or two barrier methods) while on study and for at least 3 months following the Plerixafor infusion		
	Exclusion Criteria (From IRB approved protocol)		
1.	Prior or concurrent treatment with Avastin (bevacizumab).		
2.	Prior exposure to Plerixafor.		
3.	Prior use of other investigational agents to treat the brain tumor.		
4.	Recent history of myocardial infarct (less than 3 months) or history of active angina or arrhythmia.		

	5.	Prior malignancy except previously diagnosed and definitively treated more than 3 years prior to trial or whose prognosis is deemed good enough to not warrant surveillance.				
	6.	Prior sensitivity to Plerixafor.				
	7.	Pregnant or patients who are breastfeeding				
IV. Sta	*All subject files must include supporting documentation to confirm subject eligibility. The method of confirmation can include, but is not limited to, laboratory test results, radiology to results, subject self-report, and medical record review. *V. Statement of Eligibility*					
	This	s subject is [] for partic	ipation in th	ne study.	
	Sig	gnature:		Date	:	
	Pri	inted Name:				

APPENDIX B: Protocol Pre-review Checklist

No	Description	Yes	No
1	Protocol is in the appropriate template for either Interventional or		
	Non-interventional study		
2	Title page includes names and addresses of Principal Investigator,		
	Co-investigators, Biostatistician and Coordinator as appropriate		
3	Sponsor information is included if appropriate		
4	Title page includes protocol version and date		
5	Protocol document has page numbers		
6	Schema is legible		
7	List of Abbreviations is relevant to this protocol		
8	Table of contents is complete		
9	Instructions in the template are deleted		
10	Section titles are appropriately designated and numbered		
11	All the sections in the template are complete		
12	Study calendar is complete		
13	Protocol contains adequate background/rationale information		
14	Objectives and measurements of outcome are clearly stated		
15	The sections on objectives, eligibility, outcome measurements,		
	statistics and study calendar are consistent		
16	Monitoring plan refers to Stanford DSMC		
17	Statistical section is appropriate for this study		
18	Appropriate references are included		
19	Protocol includes eligibility checklist		
20	Protocol includes questionnaires as needed		
21	Protocol includes CRF statement		
22	Protocol document is well organized		

Note: Some of the requirements are applicable to only **Interventional** studies as specified in the template.
